#### Describe what will happen to the subject solely for the purpose of this research study:

The **child participant** will undergo randomization, prospective health data collection, and pain/anxiety assessments related to VAD placement (1 anxiety survey before and 1 repeat anxiety survey with pain rating after VAD placement) solely for the purpose of this study.

The **adult participant (parent/guardian)** would complete anxiety assessments related to their child's VAD placement (1 survey before and 1 repeat survey after placement) and agreement to participate in a semi-structured interview after the VAD is removed. The child participant is welcome to contribute to the semi-structured interview responses with the parent as a child-parent dyad, but the child is not required to do so as part of the study.

The parent and child will be given the first survey to fill out prior to VAD placement. The study team member will distribute and collect the first survey. The repeat survey will be placed in the patient's binder. Following VAD placement (and once child is fully alert if sedation was used during placement), the study team member will either (1) return to distribute the repeat surveys to the family, or if unable (e.g. VAD is placed after business hours) (2) will Voalte the bedside nurse to hand the repeat survey papers to the guardian and child, and store them in the patient's binder upon completion. The study team member will collect the second completed surveys from the families. The study team member will enter the paper survey data into the REDCap database form associated with the participants, and then shred the paper versions. **Describe what is happening per protocol but is considered part of routine care (would happen even if the individual did not participate):** 

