#### Risks

A. Describe potential research-related risks and discomforts (consider physical, psychological, legal, social/economic/financial, loss of confidentiality, group harms); describe the probability, magnitude, and duration of the potential risks; do not address risks that would be present if the individual did not participate:

Physical risks: The subjects included in this study require VADs for medical treatment, which poses risks for complications and hospital-acquired conditions. Since it is not yet clearly known whether one VAD is more effective than the other in pediatric patients, the research randomization process could introduce physical risks that may not have occurred if the opposite VAD was selected by the medical team.

(1) Based on available literature, LPCs are safer than PICCs with fewer significant side effects (VTE, CLABSI) because they don't enter the central circulation. However, because LPCs are peripheral VADs (similar to a regular peripheral IV) they may not last as long as a PICC. Patients randomized to the LPC arm may be at higher risk for needing VAD replacement due to early catheter failure.

(2) VADs are sometimes used for lab draws to avoid extra poke to the patient. Both PICCs and LPCs can be used for lab draws; however, it is unknown if LPCs can sustain as many lab draws as PICCs before catheter failure.

(3) Most PICCs are placed under sedation while LPCs are placed awake. Randomization to the LPC arm would prevent the risks associated with sedation (e.g., nausea/vomiting, confusion). However, because the LPC will be placed in an awake patient (similar to a regular peripheral IV), there would be pain/discomfort with the placement, but this discomfort would be short lived (most discomfort is while the needle is inserted which takes a few seconds) and minimized using established comfort measures. Any other physical risks are expected to be comparable to ordinary medical care.

Psychosocial risks: Subjects and their guardians may feel discomfort participating in the structured interview about their experience with the VAD. Discomfort could arise from recalling stressful experiences during the child's hospitalization. These risks are expected to be comparable to ordinary life.

Privacy risks: Data security breaches could risk a loss of privacy for subjects included in this study.

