#### D. Describe procedures to be employed in analyzing data (including a power analysis):

Quantitative. Study data will be collected using REDCap. Feasibility outcomes will be collected from (1) screening logs maintained by the study team (rate of enrollment, assigned intervention), (2) ease/difficulty of VAD placement (scale 0=worse to 10=best) to determine VAD acceptability, and (3) REDCap datasheet for assessing missed data. Patient demographics (age, gender, race/ethnicity), clinical factors (reason for admission, co-morbidities, reason for PICC/LPC request, therapy to be infused, requesting service, hospital floor), VAD data (VAD type and size placed, insertion site/vessel, sedation, number of attempts, additional VADs), effectiveness data (time-to-removal of VAD, prolonged NPO, number of lab draws from VAD, number of non-VAD blood draws) and complications requiring medical intervention will be collected using the EMR and daily (Monday-Friday) check-ins with the bedside nurse. Procedural pain with non-sedated VAD placement will be assessed in patients age > 5 years by the RC within 24 hours of insertion using the Faces Pain Score (FPS) or the 0-10 pain scale depending on the developmental age of the patient. Patient/parent anxiety and overall experience with VAD placement will be assessed on a 0-10 scale (0= lowest, 10=highest) and using the short State-trait anxiety inventory (STAI) that is validated in children 5 and older.

Descriptive statistics will be used to report feasibility outcomes and explore clinical factors (see above). Cross over rate will be calculated as the proportion of the number of subjects who crosses from the randomized arm/line to a different arm/line. The exact Clopper-Pearson 95% confidence interval will be generated. Time-to-device removal for all reasons will be compared using a t-test. Non-inferiority of LPCs to PICCs will be demonstrated if the 95% confidence interval of the mean difference lies above -1 (non-inferiority margin: 1 day). The remaining outcomes will be compared using Chi-square test or Fisher's exact for categorical variables and t-test or Mann-Whitney-Wilcoxon test for continuous variables. Where necessary for parametric assumptions, appropriate transformations will be employed. Non-parametric tests will be used where parametric assumptions are not satisfied. Logistic regression or general linear model will be performed to control the potential confounders.

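### Pain is rated only in awake placements, but sedation follows the assigned device, so a between-arm test of awake-only pain would not be a randomised comparison

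*Combined protocol and SAP*

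**What the plan says.** **Who is rated.** Section 6 D (data analysis) reads: "Procedural pain with non-sedated VAD placement will be assessed in patients age > 5 years by the RC within 24 hours of insertion".

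**How pain would be analysed.** Pain has no analysis of its own. After the analyses for feasibility, cross-over and time to removal, Section 6 D adds a general rule: "The remaining outcomes will be compared using Chi-square test", or Fisher's exact test, for categorical variables, with a t-test or Mann-Whitney-Wilcoxon test for continuous ones. Pain is not excepted. Adjustment is equally general: "Logistic regression or general linear model will be performed to control the potential confounders". No covariate is named.

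**Sedation by arm.** Risks A, item 3: "Most PICCs are placed under sedation while LPCs are placed awake". Table 1 in the Background lists sedation as common for PICCs and not used for LPCs. The Risk Level 2 rationale in Section 8 E also describes PICC placement as generally sedated.

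**The survey procedure.** Section 1 F gives the child "1 anxiety survey before and 1 repeat anxiety survey with pain rating after VAD placement". The repeat survey is handed over after placement, "and once child is fully alert if sedation was used during placement". It does not say whether a sedated child completes the pain item.

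**The concern.** Randomisation makes the two groups of 35 comparable. It does not make comparable whichever subsets of them happen to be placed awake. Sedation is decided after the device is assigned, and it depends strongly on that device. Restricting to awake placements keeps nearly the whole LPC group and a selected part of the PICC group.

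If PICC children placed awake tend to be, say, calmer or more tolerant of needles, the test would show LPCs as more painful even if the device made no difference. If they tend to be more prone to pain, it would show the reverse.

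At stake is how a pain p-value is read. Risks A names discomfort from awake placement as a consequence of LPC assignment, so the outcome is worth reporting. The pilot is also meant to supply baseline estimates for a full-scale trial, and an unlabelled p-value could be carried forward as a randomised result.

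**Working it through.** **The plan's own figure.** The only precision figure is for participation: 1.96 × √(0.70 × 0.30 / 60) = 0.116, which agrees with the stated ±12%. It has no bearing on pain, for which the plan gives no figure.

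**Inputs.** From the documents: 35 children per arm, 1:1 allocation, LPCs placed awake. Assumed: PICC sedation *s* of 50%, 69% or 90%. The documents give no local sedation rate. The 69% is the PICC general-anaesthesia rate in the cystic fibrosis trial cited in the Background (10% for LPCs there), used only as a stand-in.

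**Step 1: how many PICC children are rated.** Awake PICC children = 35 × (1 − *s*). The 95% half-width, in SD units, is 1.96 × √(1/n_PICC + 1/35). For 35 against 35 it is 1.96 × √(2/35) = 0.47 SD.

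| PICC sedation (assumed) | PICC rated | LPC rated | Half-width | Standard error relative to 35 vs 35 |
|---|---|---|---|---|
| 50% | 17.5 | 35 | 0.57 SD | 1.22 |
| 69% | 10.9 | 35 | 0.68 SD | 1.45 |
| 90% | 3.5 | 35 | 1.10 SD | 2.35 |

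The age limit lowers these counts. In the local LPC series (Preliminary work) the lower quartile of age is 7 years, so about 75% or more exceed 5. If that share held here, 35 × 0.75 ≈ 26 per arm would be age-eligible, leaving about 13, 8 or 3 PICC children against 26 LPC children. That series is 20 LPCs in 19 patients, not PICC candidates, so the share is also an assumption.

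**Step 2: how selection alone could shift the result.** Suppose the decision to sedate depends on a trait with correlation ρ to pain, and that the PICC children highest on tolerance are the ones placed awake. With no true device effect, the expected LPC-minus-PICC difference is ρ × φ(z)/(1 − *s*) SD, where φ is the standard normal density and z its *s*-quantile. At *s* = 69% the multiplier is 1.138, so the shift is 0.23, 0.34 or 0.57 SD at ρ = 0.2, 0.3 or 0.5. If ρ changes sign, so does the shift.

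**Step 3: false-positive rate.** Simulated null trials, 69% vs 0% sedated, two-sided 5% t-test:

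| Assumed ρ | 26 per arm (age-eligible) | 35 per arm |
|---|---|---|
| 0 | about 5% | about 5% |
| 0.2 | about 8% | about 9% |
| 0.3 | about 13% | about 16% |
| 0.5 | about 27% | about 36% |

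With 26 per arm and ρ = −0.3 the rate is again about 13%, with the shift reversed.

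**Step 4: does the planned adjustment help?** Sedation is constant in an awake-only sample, so it cannot be a covariate. Age removes bias only as far as age explains the decision to sedate. In the same simulations (26 per arm, ρ = 0.2, 0.3, 0.5), adding age brought the rate back to about 5% when age carried the whole link, to 6%, 7% and 12% when it carried half, and changed nothing when it carried none.

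**The case against.** **The test is inferred.** Pain is not named in any test, Aim 3 is worded as description, and the protocol says that the study is not powered for statistical significance. All true. Yet the catch-all sentence covers pain as written, and nothing takes it out.

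**The size is hypothetical.** This stands in full. The documents give no local sedation rate, no rule for when a PICC is placed awake, and no link between sedation and pain. The false-positive figures illustrate an assumed mechanism. If sedation is unrelated to pain-proneness there is no bias, only a small PICC group.

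**A reader might infer that the two sections contradict each other** on who is rated, who collects the rating and when. The documents do not support that. Section 1 F itself refers to Section 6 for the pain and anxiety assessments, so Section 6 D is the specification. The clause on alertness times the whole repeat survey, which also carries anxiety. After hours the study team "will Voalte the bedside nurse to hand the repeat survey papers to the guardian and child", but the nurse only distributes and stores the paper; the study team collects it and enters the data. Section 1 F gives no time window and Section 6 D supplies one. What is left is that Section 1 F does not say whether sedated children complete the pain item. Survey details are also said to be in the consent and assent forms, which are not available here, so even that silence is limited to the text at hand.

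**A reader might also infer that pain must be compared in all children by assigned arm.** That comparison keeps randomisation, but it answers a different question. If sedation lowers later ratings by an assumed 0.25, 0.5 or 1 SD, simulation (26 per arm, 69% vs 0% sedated, no other difference) gives rejection in about 9%, 23% or 64% of trials. That is a real effect of device plus sedation, not of awake insertion pain. It is a choice of estimand and not a correction.

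**Conclusion.** The point holds as a minor one. As written, the plan would apply a between-arm test to pain in awake placements only. That is not a randomised comparison, and no covariate adjustment makes it one. This conclusion rests on the text alone: the restriction to non-sedated placements, sedation that follows the arm, and a catch-all test that does not exempt pain.

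The size rests on assumptions. With PICC sedation of 50% to 90%, the PICC group falls to between 17.5 and 3.5 of 35 before the age limit. Bias arises only if the choice to sedate is related to pain-proneness, and neither its direction nor its size can be taken from the documents. It would be wrong to conclude that the pain result must favour one device.

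One secondary Aim 3 outcome is affected. The feasibility criteria and the time-to-removal comparison are not.

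**What to change.** 1. In Section 6 D, exclude awake-only procedural pain from the catch-all between-arm tests.
2. Report it descriptively by arm, without a p-value, labelled as a non-randomised comparison, with the number sedated and the number rated in each arm.
3. In Section 1 F, state the same rated population as in Section 6 D, so that it is clear whether a sedated child completes the pain item.

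If the sponsor wants a between-arm pain test, it should use ratings from all randomised children within the age limit, compared by assigned arm, and say that the result describes the device together with its sedation and not awake insertion pain. That is the sponsor's choice and is not required. It would mean collecting ratings from sedated children as well.

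**Cost.** The required part is wording only. Sedation is already recorded, no instrument is added, and sedation practice is untouched. What is given up is a p-value for awake pain.

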#### C. Hypothesis/specific aims:

The aims of this pilot, randomized controlled trial are:

*Aim 1:* To assess the feasibility of a full-scale effectiveness trial comparing PICCs to LPCs in hospitalized pediatric patients in need of non-central, medium-term vascular access (5-14 days anticipated need). *Hypothesis:* Feasibility of a full-scale effectiveness trial will be established by demonstrating that > 70% of eligible patients agree to enrollment and randomization, > 80% of randomized patients receive the assigned intervention, > 80% of providers involved find the study acceptable, and < 5% of data are missing.

*Aim 2*: To identify a population in which a LPC is a safe and effective alternative to a PICC for vascular access in hospitalized pediatric patients age > 2 years, in need of non-central, medium-term access. *Hypothesis:* We hypothesize that LPCs are non-inferior to PICCs for delivery of peripherally compatible infusate needed for 5-14 days in hospitalized pediatric patients. We plan to determine the time-to-removal of the vascular access device, both secondary to completion of therapy and secondary to complications. Safety will be assessed by measuring complication rate (e.g., VTE, CLABSI, occlusion, dislodgement, phlebitis). Cross over rate will be closely monitored as well.

*Aim 3:* To engage patients and families as advisors in vascular access device selection. We will describe the patient and family experience with device placement and maintenance as well as perceived patient and parent insertion-related and sedation-related distress.

D. Background, significance, and rationale (including description of preliminary studies and any results):

Many hospitalized children require a vascular access device (VAD) for delivery of life saving interventions such as intravenous fluids and antibiotics.[1] With the broad range of VADs available, and their different profile of complications,[2] it is essential that clinicians have access to rigorous evidence to guide the selection of the most appropriate VAD. Appropriate VAD selection results in treatment efficiency and a decrease in catheter-related complications.[1] The problem is, even the most current and comprehensive guideline for VAD selection published in 2020, the Michigan Appropriateness Guide for Intravenous

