rate and cross-over rate will be conducted after enrolling 20 and then again after enrolling 40 out of the 70 participants. Participants' length of hospitalization is not dependent on the study participation and discharge criteria will be determined by their primary medical team. In case of a serious complication related to the VADs, the planned rescue intervention is to remove the VAD and treat the complication per routine clinical care. The primary attending physician will guide treatment of any catheter related complications in collaboration with the treating team. Treatment of catheter-related complications will not be the responsibility of the research team. Both VADs included in this study are regular standard of care at Children's Wisconsin, and treating their complication falls within the responsibility of the primary medical provider taking care of that patient. A comprehensive list of catheter related complications [36] are provided in the table below. Some of the complications (e.g., phlebitis and infiltration) are graded based on severity following established guidelines per the Infusion Therapy Standards of Practice.[36] Complications are divided into major (serious complications that generally require treatment) and minor complications (less serious complication that don't generally require treatment).

The proposed study is a feasibility pilot trial and not powered to detect a difference in efficacy between groups, therefore, efficacy stopping rules can't be established. See safety stopping rules below.

Complications	Definition
Major	·
Central line associated bloodstream	NHSN surveillance definition: A laboratory confirmed infection
Infection (CLABSI)	where a LVC is in place for >2 calendar days prior to a positive
	culture
Catheter-associated blood stream	A bloodstream infection (BSIs) originating from either
infection (CABSI)	peripheral intravenous catheters (PIVCs) and/or central
	vascular access devices.
Catheter- related blood stream	It is diagnosed if the same organism is isolated from a
infection (CR-BSI)	blood culture and the tip culture, and the quantity of
	organisms isolated from the tip is greater than 15 colony
	forming units (CFUs). Alternatively, differential time to
	positivity (DTP) requires the same organism to be isolated
	from a peripheral vein and a catheter lumen blood culture,
	with growth detected 2 nours sooner (ie, 2 nours less
	incubation) in the sample drawn from the catheter.

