# C. Have stopping rules been established for the study (to evaluate whether the objectives have been met, or that the objectives cannot be met, or that the accumulated data indicates that the risks exceed the benefits of the study)?

#### □No ⊠ Yes □ N/A (study is not greater than minimal risk)

If YES, describe the stopping rules: The study will be stopped so the protocol can be re-evaluated for the following reasons: (1) catheter-related bloodstream infections identified in > 5 patients per arm (~15% of cohort), (2) catheter related venous thromboembolism identified in > 5 patients per arm (~15% of cohort), (3) catheter failure rate (meaning catheter had to be removed prior to completion of therapy intended for) > 50%, (4) cross-over rate > 30%. Those stopping rules will be assessed continuously from the time first patient is enrolled until study completion.

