The study is not powered to detect statistical significance, but rather to assess the feasibility of this study protocol for a larger full-scale effectiveness trial and provide baseline estimates for the sample size calculations. With a sample size of 60 or more patient subjects, we will be able to estimate a participation rate of 70% (eligible patients agree to enrollment and randomization) within a 95% confidence interval of +/- 12%.

Qualitative. We will perform semi-structured interviews in a subgroup of the study participants; the adult guardians will be asked to participate as research subjects. We anticipate interviewing up to 35 participants from each randomized study group (70 total), but sample size will be determined by data saturation. Interviews will be completed by the research team within the week following completion of therapy, either in person (if the patient is still hospitalized) or via phone (if the patient was discharged). The main purpose of the interviews is to understand the patient's and family's lived experience with device insertion and ongoing maintenance during the time of participation in the study. The child is welcome to participate in the interview with their adult guardian but not required to. Their advice on ways to improve the process of insertion and/or maintenance will be collected as well. Interviews will be audio-recorded, transcribed verbatim, and uploaded into MAXQDA Qualitative Analysis software for coding. We will use a team-based inductive coding strategy, followed by theme identification.

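### The only decision rule for Aim 2 judges non-inferiority on mean all-cause dwell time against an unexplained 1-day margin, so it does not directly measure delivery of the intended therapy and would probably return an uninformative verdict

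*Combined protocol and SAP*

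**What the plan says.** Aim 2 (Section 1, part C) hypothesises that "LPCs are non-inferior to PICCs for delivery of peripherally compatible infusate needed for 5-14 days". It continues: "We plan to determine the time-to-removal of the vascular access device, both secondary to completion of therapy and secondary to complications".

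The quantitative analysis (Section 6 D) has one decision rule for this aim: "Time-to-device removal for all reasons will be compared using a t-test. Non-inferiority of LPCs to PICCs will be demonstrated if the 95% confidence interval" meets a stated bound. The bound is that the interval "of the mean difference lies above -1 (non-inferiority margin: 1 day". No section explains why 1 day was chosen. All remaining outcomes are assigned generically to chi-square or Fisher tests if categorical, and to t or rank tests if continuous.

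The stopping rules (Section 6 C) define an event closer to the Aim 2 question: "catheter failure rate (meaning catheter had to be removed prior to completion of therapy intended for". The monitoring plan (Section 6 B) schedules analysis of complication, failure and cross-over rates after 20 and 40 participants.

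On purpose, Section 6 D says "The study is not powered to detect statistical significance, but rather to assess the feasibility of this study protocol" and that the pilot is to "provide baseline estimates for the sample size calculations". Section 6 B adds: "The proposed study is a feasibility pilot trial and not powered to detect a difference in efficacy between groups".

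**The concern.** A catheter removed because treatment is finished has done its job. One removed early for occlusion or dislodgement has not. The pooled mean records only the day of removal, and longer dwell always scores better. If removal at completion is prompt, the difference in means does reflect failures, but each counts by how early it occurs, and the spread of planned course lengths adds noise unrelated to device performance.

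Three things follow. The rule does not directly measure whether the needed infusate was delivered. The margin does not tell the reader how many extra failures it accepts. And a pass/fail verdict is attached to a study whose stated product is feasibility and planning estimates. At stake is the use of the result: a negative verdict could be read as evidence against LPCs when it says little, and a positive one could be carried into the full trial without anyone having stated what loss was judged acceptable.

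**Working it through.** **The plan's own figure.** The only numerical sample-size justification is +/-12 points for a 70% participation rate with 60 patients: 1.96 x sqrt(0.7 x 0.3 / 60) = 0.116. It reproduces. No sample size or power is stated for the non-inferiority comparison.

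**Inputs from the documents.** 35 per arm (Section 3 A); margin 1 day and 95% CI (Section 6 D), taken as two-sided; anticipated course 5-14 days (inclusion criteria); PICC completion of therapy 80-90%, so failure 10-20% (Section 8 E, Risk Level 2 rationale); published LPC dwell SD 6 days (Background); local LPC dwell IQR 3-11 days (Preliminary work), giving 8/1.349 = 5.9 if normal.

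**Assumptions, not in the documents.** Planned course T uniform on 5-14 days; prompt removal at completion; a fraction f of devices fails, at a time uniform over the course.

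**1. The margin in failures.** Mean course = (5 + 14)/2 = 9.5 days. An evenly timed failure loses 9.5/2 = 4.75 days on average, so a 1-day deficit equals 1/4.75 = 0.21, or 21 extra failures per 100. Timing matters greatly: failures all in the first half give 1/(9.5 x 0.75) = 14 per 100, and all in the second half 1/(9.5 x 0.25) = 42. These are two illustrations, not bounds.

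**2. Precision.** Half-width = t(0.975, 68) x SD x sqrt(2/35) = 1.9955 x 0.2390 x SD = 0.477 x SD. It exceeds 1 day when SD > 1/0.477 = 2.1 days.

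**3. Plausible SD.** E[T^2] = (14^3 - 5^3)/(3 x 9) = 97. With failure fraction f, the mean is 9.5(1 - f/2), the second moment is 97(1 - 2f/3), and the SD is sqrt(second moment - mean^2).

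**4. Chance that identical devices meet the rule.** This is P(T' > 1.9955), where T' is noncentral t with 68 df and noncentrality 1/(SD x 0.2390).

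| Case (same in both arms) | SD (days) | Half-width (days) | Rule met |
|---|---|---|---|
| No failures | 2.60 | 1.24 | 35% |
| 10% failure | 3.01 | 1.44 | 28% |
| 15% failure | 3.18 | 1.51 | 25% |
| 20% failure | 3.31 | 1.58 | 24% |
| SD 6 from Background | 6.00 | 2.86 | 10% |

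The last row is a pessimistic reference only: that SD, like the local IQR, describes LPCs not restricted to 5-14-day courses (the local series includes a 41-day dwell).

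**5. Precision of the alternative.** The risk-difference half-width is 1.96 x sqrt([p1(1 - p1) + p2(1 - p2)]/35). At 10% v 15% it is 0.155 (about 16 points); at 20% v 45% it is 0.211 (21 points). The 45% is the share of the first 20 local LPCs that did not remain until therapy completion.

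**The case against.** The strongest case for the plan is that all-cause dwell is a legitimate pragmatic endpoint, the study openly says it is not powered, and feasibility is Aim 1. That stands, and the small sample is not the error. Several stronger readings are tempting, but the documents do not support them.

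- *The plan contradicts itself on reporting by reason.* Aim 2's wording most naturally means time to removal for each reason, but it can be read as counting removal for either reason. This is an ambiguity.
- *Failure is ignored.* The remaining-outcomes sentence can cover failure and complication proportions, and failure rate is reviewed for safety. Nor do the stopping rules say that their definition governs the effectiveness analysis. What is missing is failure in the non-inferiority rule.
- *An unpowered rule invites false claims.* The wording is conditional, and low power does not inflate false non-inferiority. The tension is between a verdict and an estimation purpose.
- *Removal habits would favour LPCs.* Different removal practice after completion could move the mean, but nothing in the documents suggests LPCs would be kept longer. The uncertainty about lab draws under Risks would, if anything, point towards PICCs being kept longer. This is illustration only.

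**Conclusion.** The point holds and should be fixed. Three parts rest on the text alone: the only Aim 2 verdict pools reasons for removal, the 1-day margin has no stated rationale, and failure before completion is defined in the plan but is outside the verdict.

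The sizes rest on the assumptions listed with the calculation. With evenly spread failures the margin corresponds to about 21 extra failures per 100, against an expected PICC failure of 10-20%. At 35 per arm the rule would be met only about 24-35% of the time by identical devices, so the likely outcome is 'not demonstrated' whether or not the devices differ. The exchange rate between days and failures is sensitive to when failures occur. The conclusion on precision is less fragile: the assumed spread of course lengths alone, with no failures, already takes the half-width past the margin.

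**What to change.** In Section 6 D:

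- (a) Make the key Aim 2 estimate the proportion of randomised children, by arm, whose first device was removed before completion of the intended therapy, using the stopping-rule definition. Report it as a risk difference with 95% CI, for planning the full trial.
- (b) Keep time to removal, reported by arm as a difference with 95% CI and also by reason for removal. This settles the Aim 2 ambiguity.
- (c) Replace the sentence on demonstrating non-inferiority with estimation wording, and require any margin carried to the full trial to be justified by the number of extra failures accepted.

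Cumulative incidence with completion as a competing event is an optional addition. Naming reason for removal and planned course length among the data items is a minor clarification, since the aims, monitoring plan and eligibility criteria already imply them.

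The cost is analysis wording; visits, sample size and care do not change. The downside is a wide risk-difference interval, about +/-16 to 21 points, so the pilot gives an estimate and not a claim. That matches its stated purpose.
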